## **Data Analysis**

Primary outcomes are measured for all participants at baseline, at three months, and after six months. We estimate the necessary sample size based on analysis of a pretest-posttest control group design. The final analysis of the data will, in addition to this approach, use a mixed-effects model. These models allow us to assess whether other factors, such as a participant's age or the patient's level of disability, are related to the measured outcomes.

Randomization will likely lead to slightly different group sizes in the study arms because participants are independently assigned to the arms, but we are not concerned about this as group sizes will also be different due to expected drop outs in each group. Once assigned to a study arm, participants will be considered in the study and we will primarily follow an intention-to-treat (ITT) approach, both for ANOVA and the mixed-effects modeling approach described below. Individuals will be included in their assigned group even if they do not participate in some or all of the intervention components (i.e., does not comply with the “treatment”).

The benefit of ITT is twofold. First, we do not bias the result by defining “sufficient compliance” with the treatment/intervention after data are collected. Second, we assure that our study result is relevant in the sense that any effect of the intervention is actually achievable with the level of encouragement to stay in the intervention as provided in this study. Especially, potential future benefits from the intervention will *not* be conditional on future participants who comply fully with the advised meetings and exercises, even in case many individuals have difficulties in study compliance.

Having said that, we will record the level of participation for each individual in each intervention arm (number of sessions that the individual participated in), and we will investigate the importance of this compliance. We expect that compliance will be an important indicator of how engaged an individual was, and how much of the offered support or education an individual could benefit from. This is an exploratory part of our data analysis.

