A second data analysis strategy will be to analyze data for only those participants who complete the study, which is an efficacy analysis. This introduces a self-selection bias, and statistical power is diminished by loss to follow-up during the course of the study. However, our estimates of treatment effects are unbiased by random attrition. The chief advantage of this primary data analysis strategy is that it has increased ability to document positive findings for participants able to maintain compliance with the intervention. However, when analyzing efficacy it is especially important to document any differences between participants who completed the study and those who were either withdrawn or lost to follow-up. Baseline demographic and clinical characteristics will be compared between completers and non-completers using chi-square tests for contingency tables, or independent-samples t-tests, as appropriate.

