### **Sample Size and Statistical Power**

Study participants will be randomly assigned to one of two arms: 1), the Individual Sessions arm, and 2) the Education Webinar arm. Hypothesis testing will compare Education Webinar arm pre-post outcomes, and Individual Sessions arm data to that of the Education Webinar arm. In accordance with the study hypotheses, our power analysis calculations are based on pretest-posttest gain score difference between contrast groups analyzed using repeated measures analysis of variance testing for a significant group by time interaction effect. Power analysis calculations use reliability data in estimating variance of gain scores (38,73,75). We base our power calculations on ANOVA because the “research on power analysis for mixed models is sparse” (105).

Power analysis assumptions used in computations included equal sample sizes in each contrast group of the study, equal variances and attrition in each contrast group, probability of Type I error of 0.05, non-directional testing of null hypotheses, and test-retest reliability as established by prior research (Table 2). Sample estimates of population parameters are assumed to be normally distributed with a mean error of zero. Accordingly, eighty or more subjects will be randomized to each arm of the study allowing attrition equal to 20% before the end of the study, which is the maximum we anticipate. This yields complete data for at least 60 caregivers in each arm of the study. More than 60 caregivers in a contrast group will increase statistical power above 0.80. The baseline data tabulated are values observed from our REACH and READI studies.

Table 2. Power analysis data.

Outcome Variable (Reference)	Baseline (M $\pm$ SD)	Reliability (r)	Power	Detectable Difference
Caregiver Measures				
Depression (PHQ-9) (73)	7.80 $\pm$ 5.94	0.84	0.80	1.78
Anxiety (GAD-7) (75)	7.61 $\pm$ 5.14	0.83	0.80	1.54
Burden (Zarit) (38)	17.56 $\pm$ 9.74	0.88	0.80	2.92

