The values tabulated in the Detectable Difference column of the table document the minimum true between contrast group difference in gain scores in population data sampled needed for statistical power to attain 0.80 or better to reject a false null hypothesis of no group by time interaction effect in repeated measures data. In general terms, we will have statistical power of 0.80 or better to reject a false null hypothesis when the between contrast group difference in gain scores attains approximately 0.30 or more of the population standard deviation estimated from REACH and READI study baseline data. For statistically significant comparisons, effect size of  $d \geq 0.2$  will be considered clinically significant, consistent with psychosocial interventions' small to medium effect sizes (46). Interaction effect sizes will be estimated as mean between-group gain score change relative to estimated population standard deviation (106).

**Mixed-Effects Modeling Approach.** Randomization into the two arms, respectively, guarantees that individuals are not systematically assigned to one arm. Regardless, when analyzing the data it should be beneficial to account for the actually present covariates for the individuals. In addition, the mixed-effects modeling approach allows us to incorporate individuals in the study who are lacking the final outcome measurements after six months. Furthermore, we can utilize all the information from the data and can utilize the post-intervention measurements for the individuals.

We will fit separate mixed-effects models for each of the primary outcomes. For each of the  $i = 1, \dots, 160$  individuals there are  $n_i$  measurements available (for a specific outcome). The primary outcomes are measured at baseline (B), and after three, and six months ( $t = B, 3, 6$ ). It is not essential that the measurements are taken for all individuals at the same time, but we do not elaborate on this here because the data collection is planned to follow the above timeline. If all measurements are available for an individual,  $n_i = 3$  (for each primary outcome). Each individual will have measurements for at least baseline, so  $n_i \geq 1$  for all  $i$ . In mixed-effects models "individuals borrow strength" from each other and it is therefore not required that all individuals have two or more measurements in order to fit straight lines to each individual.

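### The completers-only analysis is labelled primary against the plan's own ITT statement, and neither the deciding model nor the rule for judging Hypothesis 2 on three outcomes is stated

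*Combined protocol and SAP*

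**What the plan says.** **Analysis set.** The Data Analysis section commits first to ITT: "we will primarily follow an intention-to-treat (ITT) approach, both for ANOVA and the mixed-effects modeling approach described below". It gives two reasons: compliance is not defined after the data are in, and the result reflects what the offered intervention can actually achieve. It then adds: "A second data analysis strategy will be to analyze data for only those participants who complete the study, which is an efficacy analysis". The next sentence concedes the weakness: "This introduces a self-selection bias, and statistical power is diminished by loss to follow-up during the course of the study". Two sentences further on, the same analysis has become primary: "The chief advantage of this primary data analysis strategy is that it has increased ability to document positive findings for participants able to maintain compliance".

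**Model.** Sample size rests on a pretest-posttest design. The section adds: "The final analysis of the data will, in addition to this approach, use a mixed-effects model". Sample Size and Statistical Power bases power on the "pretest-posttest gain score difference between contrast groups analyzed using repeated measures analysis of variance testing for a significant group by time interaction effect", and explains that ANOVA was used because work on power for mixed models is sparse. Under Mixed-Effects Modeling Approach, effectiveness is judged by comparing slopes between arms. Covariates enter by forward selection guided by parameter significance, AIC and SC. The closing paragraph assumes data missing at random in the primary analysis, without naming the model in that sentence. The stated benefit of the mixed model is that it "allows us to incorporate individuals in the study who are lacking the final outcome measurements after six months".

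**Outcomes.** Hypothesis 2 names depression, anxiety and burden together. Each is a primary outcome with its own model. The error rate appears only as a power assumption: "probability of Type I error of 0.05, non-directional testing of null hypotheses". No hierarchy, adjustment or rule for combining the three is given.

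**The concern.** Three choices that should be settled before outcome data are analysed are left open or contradictory.

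1. **Which participants.** If the ITT and completers results disagree, either can be cited from the plan as primary. The text promotes the completers analysis for its ability to show positive findings, in the same paragraph that admits its bias.
2. **Which model.** Two models are kept, and one has covariates chosen from the data. The estimate that answers Hypothesis 2 is therefore not fixed in advance.
3. **What counts as success.** With three primary outcomes and no rule, a claim that Hypothesis 2 is supported has no defined error rate and no defined power.

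**Working it through.** **1. The plan's own power figure.** Inputs are from Table 2, with 60 per arm, two-sided 0.05. Gain-score SD = SD × √(2(1 − r)); power is from the noncentral t with noncentrality difference / (gain SD × √(2/n)).

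| Outcome | SD | r | Gain SD | Difference | Power, n = 60 | Power, n = 64 |
|---|---|---|---|---|---|---|
| PHQ-9 | 5.94 | 0.84 | 3.36 | 1.78 | 0.821 | 0.845 |
| GAD-7 | 5.14 | 0.83 | 3.00 | 1.54 | 0.797 | 0.822 |
| Zarit | 9.74 | 0.88 | 4.77 | 2.92 | 0.914 | 0.930 |

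The stated 0.80 reproduces, with GAD-7 as the limiting row. The 64 is 80 × 0.8, the number left after the plan's 20% attrition. These figures are for one outcome at a time.

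**2. Do gain and slope differ?** For visits at 0, 3 and 6 months, the centred times are −3, 0 and 3. A completer's least-squares slope is (−3·y0 + 0·y3 + 3·y6) / (9 + 0 + 9) = (y6 − y0) / 6. That is the six-month gain divided by 6. With complete data and compound symmetry the two contrasts are therefore nearly the same test. What separates the models is covariate selection and the treatment of participants without a six-month value. The plan says how the mixed model keeps them but not how the ANOVA would. The effect of forward selection was not quantified.

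**3. Error if any one outcome suffices.** For uncorrelated test statistics:

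- either direction: 1 − 0.95³ = 14.3%
- individual sessions falsely superior: 1 − 0.975³ = 7.3%, against 2.5% for one test

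For a common correlation ρ, with c = 1.96, the either-direction error is 1 − ∫ φ(u) [Φ((c − √ρ·u)/√(1 − ρ)) − Φ((−c − √ρ·u)/√(1 − ρ))]³ du. The directional error omits the second Φ term. The documents give no correlation, so the values below are assumptions.

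| ρ | False difference, either direction | False superiority of individual sessions |
|---|---|---|
| 0 | 14.3% | 7.3% |
| 0.6 | 11.8% | 5.9% |
| 0.7 | 10.9% | 5.5% |
| 0.8 | 9.8% | 4.9% |
| 0.9 | 8.4% | 4.2% |

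**4. Power if all three are required.** With the Table 2 differences true and ρ from 0 to 0.6, joint power is 0.60 to 0.69 at 60 per arm and 0.65 to 0.73 at 64. At ρ = 0 and 60 per arm this is 0.821 × 0.797 × 0.914 = 0.598. Error is not inflated under this rule.

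**5. Power under Holm.** Stepwise Holm, 400,000 simulated sets of t statistics, all three Table 2 differences true, ρ from 0 to 0.6:

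| Outcome | n = 60 | n = 64 |
|---|---|---|
| PHQ-9 | 0.77–0.78 | 0.80–0.82 |
| GAD-7 | 0.75–0.76 | 0.78–0.79 |
| Zarit | 0.86–0.88 | 0.88–0.91 |

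Against step 1, the loss is about 3 to 6 points per outcome. If only one outcome truly differs, its worst-case power is that of a test at 0.05/3 = 0.0167: 0.68, 0.65 and 0.82 at 60 per arm.

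**The case against.** The intended plan can largely be read from the text. ITT is given first with a full rationale, and the completers analysis is introduced as second with its bias admitted. A reader might infer that the sponsor means to headline the completers result; the documents do not support that, and a stray word is the likelier explanation. ANOVA is presented as a convenience for sizing, and the reference to a primary analysis stands in the mixed-model section, so the mixed model is fairly clearly meant. This stands as a reading of intent. It does not remove the contradictory label, and the statement that ITT applies to both models still leaves both in play.

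A reader might also infer that the two models ask materially different questions. Step 2 shows they hardly do in completers.

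On multiplicity, the plan fits a separate model per outcome, tabulates power per outcome and applies its d ≥ 0.2 criterion to each significant comparison. If each outcome supports only its own conclusion, 0.05 and 0.80 hold for each and no adjustment is forced. This is a fair reading, but the plan does not state it, and Hypothesis 2 bundles the three outcomes.

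Finally, 14.3% could be taken as the chance of wrongly declaring individual sessions superior. It is not: it counts errors in both directions. The directional figure is at most 7.3% and never reaches 10%.

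**Conclusion.** The point holds as a gap in specification; it is not an error in the power calculation. The primary label on the completers analysis contradicts the ITT commitment and should go. The documents point to the mixed model as deciding but do not say so, and its covariates are not fixed in advance.

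The consequence for Hypothesis 2 depends on a rule the plan does not give:

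- **Outcome by outcome:** no inflation and no loss of power.
- **Any one outcome:** over correlations 0 to 0.9, a false difference in either direction in 14.3% down to 8.4%, and false superiority of individual sessions in 7.3% down to 4.2% against 2.5%.
- **All three:** error controlled, but joint power of about 0.60 to 0.69 at 60 per arm instead of 0.80.

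These sizes rest on assumed equal correlations between the test statistics, on the plan's gain-score SDs, and on gain-score power as an approximation to the slope model. The change should be made before outcome data are analysed.

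**What to change.** 1. In Data Analysis, delete the word primary from the completers paragraph and state that this is a sensitivity analysis that cannot establish Hypothesis 2.
2. Name one deciding analysis: the mixed model under ITT on all randomised participants, using the slope contrast already described, with covariates listed in advance. Make the ANOVA supportive and the forward-selected models exploratory.
3. If an overall claim on Hypothesis 2 will be made, state one rule that holds overall error at 0.05 and restate power for it. Holm costs about 3 to 6 points per outcome when all three Table 2 differences are true. Requiring all three gives the joint power in step 4. Naming a single primary outcome costs no power for that outcome but makes the other two secondary. If no overall claim is intended, state that conclusions are outcome by outcome.

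All of these are text changes. No added enrolment or data collection is needed.

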### **Sample Size and Statistical Power**

Study participants will be randomly assigned to one of two arms: 1), the Individual Sessions arm, and 2) the Education Webinar arm. Hypothesis testing will compare Education Webinar arm pre-post outcomes, and Individual Sessions arm data to that of the Education Webinar arm. In accordance with the study hypotheses, our power analysis calculations are based on pretest-posttest gain score difference between contrast groups analyzed using repeated measures analysis of variance testing for a significant group by time interaction effect. Power analysis calculations use reliability data in estimating variance of gain scores (38,73,75). We base our power calculations on ANOVA because the “research on power analysis for mixed models is sparse” (105).

Power analysis assumptions used in computations included equal sample sizes in each contrast group of the study, equal variances and attrition in each contrast group, probability of Type I error of 0.05, non-directional testing of null hypotheses, and test-retest reliability as established by prior research (Table 2). Sample estimates of population parameters are assumed to be normally distributed with a mean error of zero. Accordingly, eighty or more subjects will be randomized to each arm of the study allowing attrition equal to 20% before the end of the study, which is the maximum we anticipate. This yields complete data for at least 60 caregivers in each arm of the study. More than 60 caregivers in a contrast group will increase statistical power above 0.80. The baseline data tabulated are values observed from our REACH and READI studies.

Table 2. Power analysis data.

Outcome Variable (Reference)	Baseline (M $\pm$ SD)	Reliability (r)	Power	Detectable Difference
Caregiver Measures				
Depression (PHQ-9) (73)	7.80 $\pm$ 5.94	0.84	0.80	1.78
Anxiety (GAD-7) (75)	7.61 $\pm$ 5.14	0.83	0.80	1.54
Burden (Zarit) (38)	17.56 $\pm$ 9.74	0.88	0.80	2.92

The values tabulated in the Detectable Difference column of the table document the minimum true between contrast group difference in gain scores in population data sampled needed for statistical power to attain 0.80 or better to reject a false null hypothesis of no group by time interaction effect in repeated measures data. In general terms, we will have statistical power of 0.80 or better to reject a false null hypothesis when the between contrast group difference in gain scores attains approximately 0.30 or more of the population standard deviation estimated from REACH and READI study baseline data. For statistically significant comparisons, effect size of  $d \geq 0.2$  will be considered clinically significant, consistent with psychosocial interventions' small to medium effect sizes (46). Interaction effect sizes will be estimated as mean between-group gain score change relative to estimated population standard deviation (106).

**Mixed-Effects Modeling Approach.** Randomization into the two arms, respectively, guarantees that individuals are not systematically assigned to one arm. Regardless, when analyzing the data it should be beneficial to account for the actually present covariates for the individuals. In addition, the mixed-effects modeling approach allows us to incorporate individuals in the study who are lacking the final outcome measurements after six months. Furthermore, we can utilize all the information from the data and can utilize the post-intervention measurements for the individuals.

We will fit separate mixed-effects models for each of the primary outcomes. For each of the  $i = 1, \dots, 160$  individuals there are  $n_i$  measurements available (for a specific outcome). The primary outcomes are measured at baseline (B), and after three, and six months ( $t = B, 3, 6$ ). It is not essential that the measurements are taken for all individuals at the same time, but we do not elaborate on this here because the data collection is planned to follow the above timeline. If all measurements are available for an individual,  $n_i = 3$  (for each primary outcome). Each individual will have measurements for at least baseline, so  $n_i \geq 1$  for all  $i$ . In mixed-effects models "individuals borrow strength" from each other and it is therefore not required that all individuals have two or more measurements in order to fit straight lines to each individual.

We build the mixed-effects models by a forward selection procedure for the covariates of particular interest to us. Because over-parameterization is a concern in this analysis, we will give priority to covariates that are individually contributing to the model fit (evaluated by significance of parameters in the model as well as AIC and SC) and are (if possible) independent of each other. To improve model fitting we will center or standardize some or all covariates. Interaction terms will be included as needed.

We investigate intervention effectiveness by comparing the slope of the linear fits for individuals that were assigned to individual sessions with the slope of individuals that were assigned to the webinars. A mixed-effects model contains *fixed effects* and *random effects*. The mixed-effects model allows us to study whether other variables are an important factor for the development of the primary outcomes. Besides the indicator of individual  $i$  intervention assignment and demographic information such as race, age, or rural/urban location, covariates of interest to us are the participant's family composition, participant gender, and the general social support the caregiver receives. We also collect the participant's perception of the patient's disability at baseline (WHODAS 2.0 level of disability from 0 to 100) and will investigate the role that covariate might play in each model. These questions will be addressed by investigating the statistical significance of the corresponding parameters in the fitted mixed-effects model. SPSS will be used for analysis.

In addition, we will investigate possible drop out patterns in the data. This is, however, an exploratory part of our analysis and we will assume that measurements are *missing at random* in the primary analysis.

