**Retention.** Because all interaction is by telephone, travel will not affect retention. We offer \$25 for each completed data collection call to offset time required (baseline, three and six months, project evaluation) for a total of \$100. In our work with spouses of post 9/11 service members, lost to follow-up rates are 17 to 20%. For our caregiver intervention studies, lost to follow-up rates are lower, around 10% (70).

**Alerts/Adverse Event Protocols.** Alerts may be recognized during data collection, outside scheduled contacts, and during intervention sessions. Alerts/adverse event standardized procedures will be those we currently use for post deployment spouses and caregivers. Alerts include suicidal ideation, increased alcohol/drug use, and clinical depression levels plus dangerous patient behaviors. Our current procedure ensures that any alert be discussed immediately with [name] and appropriate action taken, based on standardized procedures. For example, in our current study, for clinical depression levels, we follow up with the participant who is also advised to contact her physician or other resource. All alert events are recorded on the Project Alert Form that includes event date, whether event is treatment related, and date event was addressed. The form is given to [name] within 24 hours of learning of the event and the event documented by the appropriate staff member in progress notes, and reported to IRB, if appropriate. Alerts, adverse events, and referrals will not cause a participant to be dropped from the study, but will be considered in analysis. Any contact outside group or data collection will be documented (time, reason, actions taken, initiator) on the Delivery Assessment tracking form.

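### Power of 0.80 at 0.30 SD takes test-retest reliability as the baseline-to-follow-up correlation, shows no range, and leaves a more powerful baseline-adjusted test unused

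*Combined protocol and SAP*

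**What the plan says.** All points are in the combined protocol and SAP. Under Sample Size and Statistical Power, power rests on the between-arm difference in pretest-posttest gain, "analyzed using repeated measures analysis of variance testing for a significant group by time interaction effect". The gain-score variance comes from reliability: "Power analysis calculations use reliability data in estimating variance of gain scores (38,73,75". The assumptions list "test-retest reliability as established by prior research (Table 2". Table 2 gives, for each outcome, a baseline SD, one r and a detectable difference:

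- PHQ-9: SD 5.94, r 0.84, difference 1.78
- GAD-7: SD 5.14, r 0.83, difference 1.54
- Zarit: SD 9.74, r 0.88, difference 2.92

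Eighty are randomized per arm with 20% attrition allowed. On the result: "This yields complete data for at least 60 caregivers in each arm of the study". The conclusion is that "we will have statistical power of 0.80 or better to reject a false null hypothesis" at a gain-score difference of about 0.30 SD.

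The Mixed-Effects Modeling Approach retains participants, to "incorporate individuals in the study who are lacking the final outcome measurements after six months", and defines the treatment contrast thus: "We investigate intervention effectiveness by comparing the slope of the linear fits". Baseline is one of the outcome points in that model, and the baseline outcome score is not among the listed covariates. The Retention paragraph says that in the team's caregiver studies "lost to follow-up rates are lower, around 10% (70".

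**The concern.** The variance of a gain score depends on how strongly the baseline score correlates with the later score in the trial's own participants over the trial's own interval. Test-retest reliability describes how well a scale repeats when the underlying state is assumed stable. Over 3 to 6 months caregivers' true levels can move, and can move differently from person to person, so the correlation can be lower than the reliability. It would not be expected to be higher.

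The documents identify no r as coming from a 3- or 6-month interval and show no sensitivity range. Burden is less clear-cut: its r cites the reference that the Background ties to a clinical translation with 6-month follow-up, so its interval cannot be judged from the documents.

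This power statement is the only justification for 160 participants. If it is fragile, a real 0.30 SD benefit could be missed far more often than one time in five. Separately, the planned between-arm contrasts do not use the baseline score in the most efficient way.

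**Working it through.** **Inputs.** SDs, r values and differences from Table 2; two-sided 0.05; equal arms. Completers per arm: 60 (the plan's figure), 80 × 0.80 = 64 (20% loss), 80 × 0.90 = 72 (about 10% loss). Values of r other than those in Table 2 are assumptions. Equal SD at baseline and follow-up is assumed throughout.

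**Formulas.** Gain-score SD = SD × √(2(1 − r)). Baseline-adjusted (ANCOVA) residual SD = SD × √(1 − r²), with one degree of freedom fewer. Power from the noncentral t.

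**1. Reproducing the plan, 60 per arm.** Gain SDs:

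- PHQ-9: 5.94 × √0.32 = 3.36
- GAD-7: 5.14 × √0.34 = 3.00
- Zarit: 9.74 × √0.24 = 4.77

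Power at the stated differences is 0.821, 0.797 and 0.914. The exact 0.80-power differences are 1.73, 1.55 and 2.46. The three stated differences are all 0.30 SD (1.78/5.94, 1.54/5.14 and 2.92/9.74 each round to 0.300), so Table 2 is reproduced, with slack in the Zarit row.

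**2. The r needed for 0.80 power at 0.30 SD.**

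| Completers per arm | Gain score | Baseline-adjusted |
|---|---|---|
| 60 | 0.831 | 0.813 |
| 64 | 0.819 | 0.799 |
| 72 | 0.796 | 0.770 |

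Against these, 0.84 and 0.83 leave little room; 0.88 leaves some.

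**3. Power at 0.30 SD (gain score / baseline-adjusted).**

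| r | 60 per arm | 64 per arm | 72 per arm |
|---|---|---|---|
| 0.84 | 0.82 / 0.85 | 0.85 / 0.87 | 0.88 / 0.91 |
| 0.8 | 0.73 / 0.78 | 0.76 / 0.80 | 0.81 / 0.85 |
| 0.7 | 0.56 / 0.63 | 0.59 / 0.66 | 0.64 / 0.71 |
| 0.5 | 0.37 / 0.47 | 0.39 / 0.49 | 0.43 / 0.54 |

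A simulation of 8,000 trials at 60 per arm, in the order r = 0.5, 0.7, 0.8, 0.84, gave 0.380, 0.555, 0.730, 0.817 for the gain score and 0.474, 0.615, 0.773, 0.848 for ANCOVA.

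**4. Gain-score difference detectable with 0.80 power, 64 per arm.**

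| Outcome | Stated | r = 0.8 | r = 0.7 | r = 0.5 |
|---|---|---|---|---|
| PHQ-9 | 1.78 | 1.87 | 2.30 | 2.96 |
| GAD-7 | 1.54 | 1.62 | 1.99 | 2.57 |
| Zarit | 2.92 | 3.07 | 3.77 | 4.86 |

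**5. Why both planned tests leave power unused.** Since 2(1 − r) − (1 − r²) = (1 − r)², which is positive for every r below 1, the adjusted variance is always smaller. At the plan's own r and 60 per arm, power goes from 0.82 to 0.85, 0.80 to 0.83 and 0.91 to 0.93. The slope comparison does not recover this. With visits at 0, 3 and 6 months, the fitted slope is Σ(t − 3)y / 18 = (y₆ − y₀)/6, which is the month-6 gain score rescaled.

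**6. With incomplete visits.** Assume 80 per arm, 10% missing at month 3 and 20% at month 6 completely at random, equal correlations between visits, an effect growing linearly to 0.30 SD at month 6, and a normal approximation.

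| r | Slope model, separate arm baselines | Common-baseline mixed model, visit as category |
|---|---|---|
| 0.5 | 0.418 | 0.505 |
| 0.7 | 0.613 | 0.670 |
| 0.8 | 0.783 | 0.816 |
| 0.84 | 0.865 | 0.886 |

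**7. An indirect hint, of little weight.** The depression row of Table 1 (N = 125, change 0.5, SDs 1.9 and 1.7, p = .006) gives, if a paired t-test was used, t = 2.796 and SD of change = 0.5 × √125 / 2.796 = 2.00. Then r = (1.9² + 1.7² − 2.00²)/(2 × 1.9 × 1.7), or about 0.39. Rounding alone allows 0.04 to 0.64. It is a different scale in an uncontrolled group, and the test is not stated.

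**The case against.** The plan discloses its assumption, gives every input, and its result reproduces. It powers on 60 completers although 20% loss leaves 64; at 64 and its lowest r of 0.83, power at 0.30 SD is 0.82. The sources of the r values cannot be seen, so one can say that the interval is not stated, not that a wrong correlation was used. No passage supports r as low as 0.5, and the Table 1 hint is weak. If SDs shrink at follow-up in the proportion seen in Table 1, the gain-score thresholds ease to about 0.82, 0.80 and 0.78. The gain-score and slope contrasts are both valid under randomization, and against the planned mixed model the benefit of baseline adjustment is only 2 to 3 percentage points at r = 0.8 to 0.84.

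Most of this stands as a limit on the claim. It rules out asserting that the trial is underpowered. It does not supply the missing correlation or range: an unqualified claim of 0.80 power still rests on an r not shown for this follow-up. Nor does it touch the efficiency point, which holds at any r below 1, including the plan's own, and grows as r falls (about 9 points over the slope model at r = 0.5).

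**Conclusion.** The concern holds and should be fixed. The arithmetic is sound, but the conclusion is more certain than its inputs allow. For depression and anxiety, 0.80 power at 0.30 SD needs a follow-up correlation almost as high as the quoted reliability, unless attrition is nearer 10%. Burden has more margin: at 60 per arm its r can fall from 0.88 to about 0.83. Whether power is actually short is unknown, because the documents do not show the relevant correlation.

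Separately, the planned tests forgo power that the collected baseline scores would provide: about 2 to 5 percentage points among completers at r = 0.8 or above, and 7 to 11 points at r = 0.5 to 0.7. Below the thresholds in step 2, adjustment narrows a shortfall without removing it. The figures assume equal SDs over time and a true difference of 0.30 SD.

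**What to change.** 1. Specify a baseline-adjusted between-arm test: ANCOVA on the follow-up score, or a mixed model with a common baseline mean and visit as a category, in place of the raw gain-score interaction and the slope comparison. Baseline is collected before random assignment, so a common baseline mean holds by design. This must be settled before outcomes are seen by arm.

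2. Restate power and detectable differences for the planned 160. Use baseline-to-follow-up correlations observed in the sponsor's REACH and READI data, the stated source of the Table 2 baseline values, if they can be obtained. Otherwise show a range such as r = 0.5 to 0.88, labelled as assumed. State the number of completers and the equal-SD assumption each time.

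The cost is recalculation and SAP wording: no new data and no added participants. The stated detectable difference may become larger. For scale, completers per arm for 0.80 power at 0.30 SD at r = 0.84, 0.8, 0.7 and 0.5 are 57, 71, 106 and 176 with the gain-score test, and 53, 64, 90 and 132 with the adjusted test.
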